		ANCOVA with mBOCF/LOCF	ITT Population	IXE80Q2W & IXE80Q4W vs. placebo at Week 16	Other secondary efficacy analyses (Section 6.10.4)
ASSpiMRI-Berlin Score	ASSpiMRI Berlin change from baseline	ANCOVA with observed case analysis	ITT Population who participate in MRI addendum	IXE80Q2W & IXE80Q4W vs. placebo at Week 16	Other secondary efficacy analyses (Section 6.10.2)
		ANCOVA with mBOCF	ITT Population who participate in MRI addendum	IXE80Q2W & IXE80Q4W vs. placebo at Week 16	Other secondary efficacy analyses (Section 6.10.4)
ASAS	ASAS5/6 and ASAS partial remission	Logistic regression analysis with NRI; Fisher's exact test with NRI	ITT Population	IXE80Q2W & IXE80Q4W vs. placebo at Week 16 and all other postbaseline visits in Period 2	Other secondary efficacy analyses (Section 6.10.4)
		Descriptive statistics of ASAS5/6 response rate and ASAS partial remission	Extended Treatment Period Population	No treatment group comparisons during Period 3	Other secondary efficacy analyses (Section 6.10.4) This summary includes Extended Treatment Period Population overall and by ASAS20 or ASAS40 response status (responder vs. nonresponder) at Week 16 (Visit 8) (NRI)

Measure	Variable	Analysis Method (Sections 6.1, 6.3)	Population (Section 6.1.5)	Comparison/Time Point	Analysis Type
Patient Global	Patient Global change and % improvement from baseline	MMRM	ITT Population	IXE80Q2W & IXE80Q4W vs. placebo at Week 16 and all other postbaseline visits in Period 2	Other secondary efficacy analyses (Section 6.10.4)
		ANCOVA with mBOCF	ITT Population	IXE80Q2W & IXE80Q4W vs. placebo at Week 16 and all other postbaseline visits in Period 2	Other secondary efficacy analyses (Section 6.10.4)
		Descriptive statistics of change from baseline	Extended Treatment Period Population	No treatment group comparisons during Period 3	Other secondary efficacy analyses (Section 6.10.4)
Spinal Pain	Spinal Pain and Spinal Pain at night change and % improvement from baseline	MMRM	ITT Population	IXE80Q2W & IXE80Q4W vs. placebo at Week 16 and all other postbaseline visits in Period 2	Other secondary efficacy analyses (Section 6.10.4)
		ANCOVA with mBOCF	ITT Population	IXE80Q2W & IXE80Q4W vs. placebo at Week 16 and all other postbaseline visits in Period 2	Other secondary efficacy analyses (Section 6.10.4)
		Descriptive statistics of change from baseline	Extended Treatment Period Population	No treatment group comparisons during Period 3	Other secondary efficacy analyses (Section 6.10.4)
CRP	CRP change from baseline; ratio of postbaseline to baseline CRP	MMRM	ITT Population	IXE80Q2W & IXE80Q4W vs. placebo at Week 16 and all other postbaseline visits in Period 2	Other secondary efficacy analyses (Section 6.10.4)
		ANCOVA with mBOCF	ITT Population	IXE80Q2W & IXE80Q4W vs. placebo at Week 16 and all other postbaseline visits in Period 2	Other secondary efficacy analyses (Section 6.10.4)
		MMRM	ITT Population	IXE80Q2W & IXE80Q4W Starting Dose 160 mg and 80 mg during Period 2	Other secondary efficacy analyses (Section 6.10.4)
		Descriptive statistics of change from baseline	Extended Treatment Period Population	No treatment group comparisons during Period 3	Other secondary efficacy analyses (Section 6.10.4)

Measure	Variable	Analysis Method (Sections 6.1, 6.3)	Population (Section 6.1.5)	Comparison/Time Point	Analysis Type
Mobility-Related Measures	BASMI linear (incl. 5 components); chest expansion, occiput to wall distance change from baseline	MMRM	ITT Population	IXE80Q2W & IXE80Q4W vs. placebo at Week 16 and all other postbaseline visits in Period 2	Other secondary efficacy analyses (Section 6.10.4)
		ANCOVA with mBOCF	ITT Population	IXE80Q2W & IXE80Q4W vs. placebo at Week 16 and all other postbaseline visits in Period 2	Other secondary efficacy analyses (Section 6.10.4)
		Descriptive statistics of change from baseline	Extended Treatment Period Population	No treatment group comparisons during Period 3	Other secondary efficacy analyses (Section 6.10.4)
Enthesitis Scores	MASES and SPARCC change from baseline	MMRM	ITT Population with Baseline MASES >0(or SPARCC >0)	IXE80Q2W & IXE80Q4W vs. placebo at Week 16 and all other postbaseline visits in Period 2	Other secondary efficacy analyses (Section 6.10.4)
		ANCOVA with mBOCF	ITT Population with Baseline MASES >0(or SPARCC >0)	IXE80Q2W & IXE80Q4W vs. placebo at Week 16 and all other postbaseline visits in Period 2	Other secondary efficacy analyses (Section 6.10.4)
		Descriptive statistics of change from baseline	Extended Treatment Period Population with Baseline MASES >0(or SPARCC >0)	No treatment group comparisons during Period 3	Other secondary efficacy analyses (Section 6.10.4)
	MASES score = 0 (similarly SPARCC = 0)	Logistic regression analysis with NRI; Fisher's exact test with NRI	ITT Population with Baseline MASES >0(or SPARCC >0)	IXE80Q2W & IXE80Q4W vs. placebo at Week 16 and all other postbaseline visits in Period 2	Other secondary efficacy analyses (Section 6.10.4)

Measure	Variable	Analysis Method (Sections 6.1, 6.3)	Population (Section 6.1.5)	Comparison/Time Point	Analysis Type
		Descriptive statistics of MASES = 0 (or SPARCC=0)	Extended Treatment Period Population with Baseline MASES >0 (or SPARCC >0)	No treatment group comparisons during Period 3	Other secondary efficacy analyses (Section 6.10.4)
Peripheral Arthritis	TJC and SJC change from baseline	MMRM	ITT Population with Baseline TJC>0 (or SJC>0)	IXE80Q2W & IXE80Q4W vs. placebo at Week 16 and all other postbaseline visits in Period 2	Other secondary efficacy analyses (Section 6.10.4)
		ANCOVA with mBOCF	ITT Population with Baseline TJC>0 (or SJC>0)	IXE80Q2W & IXE80Q4W vs. placebo at Week 16 and all other postbaseline visits in Period 2	Other secondary efficacy analyses (Section 6.10.4)
		Descriptive statistics of change from baseline	Extended Treatment Period Population	No treatment group comparisons during Period 3	Other secondary efficacy analyses (Section 6.10.4)
	TJC = 0, SJC=0, respectively, when patients had current or historical peripheral arthritis at baseline	Logistic regression analysis with NRI; Fisher’s exact test with NRI	ITT Population with current or historical peripheral arthritis at baseline	IXE80Q2W & IXE80Q4W vs. placebo at Week 16 and all other postbaseline visits in Period 2	Other secondary efficacy analyses (Section 6.10.4)
		Descriptive statistics of TJC = 0 (or SJC =0)	Extended Treatment Period Population with current or	No treatment group comparisons during Period 3	Other secondary efficacy analyses (Section 6.10.4)

Measure	Variable	Analysis Method (Sections 6.1, 6.3)	Population (Section 6.1.5)	Comparison/Time Point	Analysis Type
			historical peripheral arthritis at baseline		
	TJC = 0 when baseline TJC >0 (similarly SJC = 0 when baseline SJC >0)	Logistic regression analysis with NRI; Fisher's exact test with NRI	ITT Population with Baseline TJC>0 (or SJC>0)	IXE80Q2W & IXE80Q4W vs. placebo at Week 16 and all other postbaseline visits in Period 2	Other secondary efficacy analyses (Section 6.10.4)
		Descriptive statistics of TJC = 0 (or SJC =0)	Extended Treatment Period Population with Baseline TJC>0 (or SJC>0)	No treatment group comparisons during Period 3	Other secondary efficacy analyses (Section 6.10.4)
Anterior Uveitis	Crude and exposure-adjusted incidence rates for patients with anterior uveitis	Fisher's exact test and Poisson regression	ITT Population	IXE80Q2W & IXE80Q4W vs. placebo during Period 2	Other secondary efficacy analyses (Section 6.10.4)
		Descriptive statistics	Extended Treatment Period Population	No treatment group comparisons during Period 3	Other secondary efficacy analyses (Section 6.10.4)
		Descriptive statistics	ITT Population Who are Initially Randomized to Ixekizumab	No treatment group comparisons during Combined Periods 2 and 3	Other secondary efficacy analyses (Section 6.10.4)
NSAID (including COX-2 inhibitors) Intake	Proportion of patients taking NSAID	Descriptive statistics	Extended Treatment Period Population	At baseline (Week 0), Weeks 16, 24, 32, 44, 52	Analyses on NSAID intake (Section 6.10.4.1)

Measure	Variable	Analysis Method (Sections 6.1, 6.3)	Population (Section 6.1.5)	Comparison/Time Point	Analysis Type
	Change from baseline in ASAS-NSAID	Descriptive statistics	Extended Treatment Period Population who have NSAID (including COX-2 inhibitor) intake at baseline	At Weeks 16, 24, 32, 44, 52	Analyses on NSAID intake (Section 6.10.4.1)
	ASAS-NSAID50; ASAS-NSAID10; ASAS-NSAID0	Descriptive statistics	Extended Treatment Period Population who have NSAID (including COX-2 inhibitors) intake at baseline	At Weeks 16, 24, 32, 44, 52	Analyses on NSAID intake (Section 6.10.4.1)

Abbreviations: ANCOVA = analysis of covariance; ASDAS = Ankylosing Spondylitis Disease Activity Score; ASAS = Assessment of Spondyloarthritis International Society; BASDAI = Bath Ankylosing Spondylitis Disease Activity Index; BASMI = Bath Ankylosing Spondylitis Metrology Index; CRP = C-reactive protein; IXE = ixekizumab; IXE80Q2W = ixekizumab 80 mg every 2 weeks; IXE80Q4W = ixekizumab 80 mg every 4 weeks; ITT = intent-to-treat; LOCF = last observation carried forward; MASES = ; mBOCF = modified baseline observation carried forward; MMRM = mixed-effects model of repeated measures; NSAID = nonsteroidal anti-inflammatory drug; NRI = nonresponder imputation; pMI = placebo multiple imputation; SJC = swollen joint count; TJC = tender joint count.

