Maastricht Ankylosing Spondylitis Enthesitis Score (MASES)	The MASES is an index used to measure the severity of enthesitis (Heuft-Dorenbosch et al. 2003). The MASES assesses 13 sites for enthesitis using a score of “0” for no activity, or “1” for activity. Sites assessed include: costochondral 1 (right/left), costochondral 7 (right/left), spinal iliaca anterior superior (right/left), crista iliaca (right/left), spina iliaca posterior (right/left), processus spinosus L5, and Achilles tendon proximal insertion (right/left).	MASES	The MASES is the sum of all site scores. Range: 0 to 13, higher scores indicate more severe enthesitis 0 = no activity and not evaluable 1 = activity	Missing if baseline or observed ASDAS score is missing
		MASES change from baseline	Change from baseline calculated as: observed MASES – baseline MASES	Missing if baseline ASDAS score or observed ASDAS score is missing
		MASES score = 0	MASES score = 0 refers to complete resolution in enthesitis Analysis of MASES score = 0 only applies to patients with baseline enthesitis (MASES >0).	Missing if >20% (ie, 3 or more) sites are missing If ≤20% missing, then imputed sum = sum of scores from nonmissing sites x 13/ no. of nonmissing sites

Description and Derivation of Primary and Secondary Efficacy Outcomes

Spondyloarthritis Research Consortium of Canada (SPARCC) enthesitis	SPARCC enthesitis is an index used to measure the severity of enthesitis (Maksymowych et al. 2009). The SPARCC assesses 16 sites for enthesitis using a score of “0” for no activity, or “1” for activity. Sites assessed include: Medial epicondyle (left/right (L/R)), Lateral epicondyle (L/R), Supraspinatus insertion into greater tuberosity of humerus (L/R), Greater trochanter (L/R), Quadriceps insertion into superior border of patella (L/R), Patellar ligament insertion into inferior pole of patella or tibial tubercle (L/R), Achilles tendon insertion into calcaneum (L/R) and Plantar fascia insertion into calcaneum (L/R).	SPARCC enthesitis	The SPARCC is the sum of all site scores. Range: 0–16, higher scores indicate more severe enthesitis.	Missing if baseline or observed value is missing
		SPARCC enthesitis change from baseline	Change from baseline calculated as: observed SPARCC enthesitis – baseline SPARCC enthesitis	Missing if observed value is missing

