		SPARCC enthesitis score = 0	SPARCC enthesitis score = 0 refers to complete resolution in enthesitis Analysis of SPARCC enthesitis score = 0 only applies to patients with baseline enthesitis (SPARCC enthesitis >0).	Missing if >20% (ie, 4 or more) sites are missing. If ≤20% missing, then imputed sum = sum of scores from nonmissing sites x 16/ no. of nonmissing sites.

Description and Derivation of Primary and Secondary Efficacy Outcomes

Tender Joint Count (TJC)	The number of tender and painful joints will be determined by examination of 46 joints (23 joints on each side of the patient’s body). The 46 joints are assessed and classified as tender or not tender.	TJC total score	Adjusted sum of the pain/tenderness for all 46 joints: $\left(\frac{\text{sum of all joints checked to be painful/tender}}{\text{number of evaluable joints}}\right) \times 46$ See Appendix 4 for details.	Missing if baseline or observed value is missing
		Proportion of patients with TJC = 0 when baseline TJC > 0	TJC > 0 refers to incidence of TJC. Analysis of TJC = 0 only applies to patients whose baseline TJC > 0.	Missing if observed value is missing
		Proportion of patients with TJC = 0 for patients with current or historical peripheral arthritis at baseline	TJC > 0 refers to incidence of TJC. Analysis of TJC = 0 only applies to patients with current or historical peripheral arthritis at baseline.	If more than half of the joint scores are non-evaluable, the total score will be missing.
		TJC change from baseline	Calculated as: observed TJC – baseline TJC only applies to patients whose baseline TJC > 0.	Missing if observed value is missing
Swollen Joint Count (SJC)	The number of swollen joints will be determined by examination of 44 joints (22 joints on each side of the patient’s body). The 44 joints are assessed and classified as swollen or not swollen.	SJC total score	Adjusted sum of the pain/tenderness for all 44 joints: $\left(\frac{\text{sum of all joints checked to be swollen}}{\text{number of evaluable joints}}\right) \times 44$ See Appendix 4 for details.	Missing if observed value is missing

Description and Derivation of Primary and Secondary Efficacy Outcomes

		Proportion of patients with SJC = 0 for patients with current or historical peripheral arthritis at baseline	SJC > 0 refers to incidence of SJC. Analysis of SJC = 0 only applies to patients with current or historical peripheral arthritis at baseline.	Missing if baseline or observed value is missing

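### MASES scores a site that could not be evaluated as 0, the same as no activity, so the site bypasses the SAP's own missing-site rule and can understate a visit score or produce an unsupported complete resolution

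*SAP*

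**What the plan says.** In SAP Section 6.10, Table RHBW.6.4, the MASES entry gives site coding as "0 = no activity and not evaluable", with 1 for activity. The score is built from those ratings: "The MASES assesses 13 sites for enthesitis" and "The MASES is the sum of all site scores", so it runs from 0 to 13. For the responder variable, "MASES score = 0 refers to complete resolution in enthesitis"; it is derived only in patients whose baseline MASES is above 0.

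The entry also has a rule for missing sites: "Missing if >20% (ie, 3 or more) sites are missing"; with fewer missing, "imputed sum = sum of scores from nonmissing sites x 13/ no. of nonmissing sites". In the extracted text this rule stands beside the resolution variable, while the rows above it refer to ASDAS. The imputation column may have slipped, perhaps in extraction. The factor of 13 shows that the rule belongs to MASES.

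Other entries in the table differ:
- Tender and swollen joint counts (TJC, SJC) divide the active joints by the evaluable joints and scale to 46 or 44. For these, "If more than half of the joint scores are non-evaluable, the total score will be missing".
- SPARCC enthesitis has a proration rule of the same kind and no line about sites that are not evaluable.

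Protocol Section 8.1.2.10 defines 0 only as no activity and gives no code for a site that could not be assessed. The SAP Revision History lists the MASES handling as a Version 2 clarification, without a reason.

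Table RHBW.6.5 analyses MASES change by MMRM and by ANCOVA with mBOCF, and MASES = 0 by logistic regression and Fisher's exact test with NRI. All of these use patients with baseline MASES above 0.

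**The concern.** A site that was not assessed carries no information about enthesitis, yet the coding gives it the most favourable value. Since 0 is a valid score, the site is not missing, and the rule written for incomplete assessments never applies to it.

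Two things are at stake. First, the level of the visit score: it can equal or fall below the prorated score, never exceed it. Second, the meaning of MASES = 0: a patient can be classed as completely resolved when the sites that still mattered were not examined. At baseline, the same coding can give a score of 0 to a patient with enthesitis and remove that patient from the analysis set.

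This also sits badly with NRI in SAP Section 6.3.1, where missing response data count as failure. Here, unobserved sites can count towards success.

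**Working it through.** **Inputs.** 13 sites, each 0 or 1; plain sum; not evaluable = 0; missing-site rule as above (all from Table RHBW.6.4). The documents give no frequency of non-evaluable sites. For illustration only, I assume a per-site probability q of 1%, 5% or 10%, independent across sites.

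**1. The SAP's own threshold.** 0.20 × 13 = 2.6, so the first whole number above 20% is 3. This agrees with the SAP. The SPARCC enthesitis threshold also reproduces: 0.20 × 16 = 3.2, hence 4.

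**2. Score level.** Compare the SAP coding with the same site treated as missing (sum × 13 / nonmissing sites for one or two, missing for three or more):

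| Sites not evaluable | Active evaluable sites | SAP coding | Missing-site rule |
|---|---|---|---|
| 1 | 4 | 4 | 4 × 13/12 = 4.33 |
| 2 | 4 | 4 | 4 × 13/11 = 4.73 |
| 3 or more | 4 | 4 | missing |
| 1 or 2 | 0 | 0 | 0 |
| 3 or more | 0 | 0 | missing |

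If non-evaluable sites are as likely to be active as evaluated ones, the expected understatement is 1/13 = 7.7% for one site and 2/13 = 15.4% for two. On the same footing, the expected score is (1 − q) of the true score: 0.99, 0.95 and 0.90 for the three values of q.

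**3. False resolution.** The total is 0 only if every evaluable site is also 0. A patient with m sites still active is scored 0 with probability q^m. For m = 1 this is 1%, 5% and 10%; for m = 2 it is 0.01%, 0.25% and 1%. In the extreme, 13 non-evaluable sites score 0 and count as resolved.

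**4. Does the missing-site rule alone cure this?** Only in part. With one or two sites missing and the rest 0, proration gives 0 × 13/12 = 0 or 0 × 13/11 = 0, which still counts as resolved. The total becomes missing only with three or more. Given that a lone active site is non-evaluable, at least 2 of the other 12 must be so too. That probability is 0.6%, 11.8% and 34.1% for the three values of q.

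**5. Change from baseline.** Take 4 truly active sites at both visits.
- Two of them not evaluable at Week 16: SAP change 2 − 4 = −2; prorated 2 × 13/11 − 4 = −1.64.
- The same two not evaluable at baseline only: SAP change 4 − 2 = +2; prorated 4 − 2 × 13/11 = +1.64.

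The error in change reverses sign with the visit at which the site is lost.

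**The case against.** The rule was added deliberately in SAP Version 2. Version 3 was approved before first unblinding, so the coding is prespecified and unambiguous. Proration also rests on an assumption that cannot be tested. Those points stand as a defence against any suggestion of data-driven choice. They do not explain why an unassessed site should count as healthy when the same entry already has a rule for incomplete assessments.

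Stronger readings are tempting, and the documents do not support them:
- A reader might infer that any active site becoming non-evaluable turns a patient into a responder. The total is a sum of 13 sites, so every other site must also score 0.
- A reader might infer that false resolution is peculiar to MASES. TJC = 0 and SJC = 0 share it: a lone active joint that becomes non-evaluable leaves 0 / evaluable joints = 0, unless more than half the joints are non-evaluable. SPARCC enthesitis is silent on such sites. Among these entries, MASES stands apart only in explicitly coding such a site as 0, which lowers the score level.
- A reader might infer a bias in favour of ixekizumab. The study is double-blind, nothing suggests that non-evaluable rates differ by arm, and step 5 shows that error in change can go either way. No bias in the treatment difference is shown.

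**Conclusion.** The point holds as a defect in a derivation rule. Visit scores are understated relative to the SAP's own missing-site rule whenever an evaluable site is active and one or two sites are not evaluable; with three or more, a total is reported that the rule would set to missing. MASES = 0 can be declared without the evidence its definition implies.

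The size per patient is modest: 4 against 4.33 or 4.73 in the examples. The 7.7% and 15.4% figures hold only if non-evaluable sites are as likely to be active as evaluated ones. The probabilities in steps 3 and 4 rest on assumed rates and independence. The number of patients affected is not given and is probably small; the effect on the comparison with placebo is unknown in size and direction.

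MASES is an other secondary endpoint with no multiplicity adjustment (SAP Section 6.10.4). No primary or major secondary result depends on it. This is a worthwhile correction of low priority.

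**What to change.** Make two short changes to the MASES entry in Table RHBW.6.4.

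1. Code a non-evaluable site as missing and apply the existing rule: prorate for one or two sites, set the total to missing for three or more. This corrects the score level and removes false resolution where three or more sites are non-evaluable.
2. For one or two such sites, state that MASES = 0 may not be declared when a site active at baseline was not evaluated at that visit.

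Neither change recovers a patient whose only active baseline sites were not evaluated: the baseline total remains 0 or becomes missing, so the patient stays outside the analysis set. Reporting the number of non-evaluable sites by arm and visit would show whether this matters; a count near zero would close the question.

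The cost is small. A few MASES values become missing, and for MASES = 0 those patients count as nonresponders under NRI. Since Week 16 was unblinded before SAP Version 4, a revised Week 16 result should be labelled a sensitivity analysis.

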Ankylosing Spondylitis Disease Activity Score (ASDAS)	The ASDAS is a composite index to assess disease activity in AS (Machado et al 2011a, 2011b; Zochling 2011). The parameters used for the ASDAS (with CRP as acute phase reactant) (Sieper et al. 2009, pg 40): 1) Total back pain (BASDAI question 2) 2) Patient global 3) Peripheral pain/swelling (BASDAI question 3) 4) Duration of morning stiffness (BASDAI question 6) 5) CRP in mg/L	ASDAS _{crp}	ASDAS _{crp} (Sieper et al. 2009, pg 41): $0.121 \times \text{total back pain} + 0.110 \times \text{patient global} + 0.073 \times \text{peripheral pain/swelling} + 0.058 \times \text{duration of morning stiffness} + 0.579 \times \text{Ln}(\text{CRP}+1)$ (Machado et al. 2015). CRP is in mg/liter, the range of other variables is from 0 to 10; Ln represents the natural logarithm. Due to the constraint of CRP, ASDAS _{crp} has a minimum score of 0.6361.	Missing if any of the component is missing. If CRP <2 mg/L or below the limit of detection, then use 2 mg/L in the calculation (Machado et al. 2015).
		ASDAS _{crp} change from baseline - major secondary outcome	Calculated as: observed ASDAS – baseline ASDAS	Missing if baseline or observed value is missing
		ASDAS Disease Activity States	Four (4) disease activity states have been defined by ASAS consensus (Machado et al. 2011c, Machado 2018): 
 • ASDAS <1.3 defines inactive disease • $1.3 \leq \text{ASDAS} < 2.1$ defines low disease activity • $2.1 \leq \text{ASDAS} \leq 3.5$ defines high disease activity ASDAS >3.5 defines very high disease activity.	Missing if observed ASDAS score is missing
		ASDAS <2.1	Defined as ASDAS < 2.1	
		Clinical important improvement	Defined as at least 1.1 unit change in ASDAS from baseline	
		Major improvement	Defined as at least 2.0 unit change in ASDAS from baseline, or reached the minimum of ASDAS score (0.6361) at post-baseline visit	

Description and Derivation of Primary and Secondary Efficacy Outcomes

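### In SAP Table RHBW.6.4 the missing-data rules sit two rows too low from ASDAS clinically important improvement to the NSAID rows, so MASES is set missing when ASDAS is missing

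*SAP*

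**What the plan says.** Table RHBW.6.4 has one row per efficacy variable. Its last column says what to do when a component is missing.

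- **MASES score.** The derivation cell reads "The MASES is the sum of all site scores", over 13 sites, and scores a non-evaluable site as 0. The missing-data rule beside it is "Missing if baseline or observed ASDAS score is missing".
- **MASES change from baseline.** The rule is "Missing if baseline ASDAS score or observed ASDAS score is missing".
- **MASES = 0.** The rule is "Missing if >20% (ie, 3 or more) sites are missing", with proration to 13 sites below that limit.
- **SPARCC enthesitis.** The 16-site counterpart, "Missing if >20% (ie, 4 or more) sites are missing", stands against SPARCC enthesitis = 0. The change row carries "Missing if observed value is missing".
- **Tender joint count (TJC).** "If more than half of the joint scores are non-evaluable, the total score will be missing" stands two rows below the TJC total. The swollen joint count (SJC) shows the same displacement.
- **ASDAS clinically important improvement.** It is "Defined as at least 1.1 unit change in ASDAS from baseline", with nothing in the last column. The major improvement row is blank there too.

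SAP Section 4 lists change in MASES and in SPARCC enthesitis as other secondary endpoints. Table RHBW.6.5 analyses both by MMRM and by ANCOVA with mBOCF, in patients with a baseline score above zero. The zero-score variables use logistic regression and Fisher's exact test with NRI.

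The Revision History (SAP Section 3) records that a two-row slip from MASES downward in this table was corrected in Version 3.

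**The concern.** ASDAS is built from BASDAI questions 2, 3 and 6, Patient Global and CRP. None of these enters MASES. The data also reach the database by different routes: an assessor examines the entheses (Protocol 8.1.2.10), patients answer on a tablet, and CRP comes from the central laboratory (Protocol 10.2.1). A lost CRP sample says nothing about the enthesis examination done at the same visit.

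Three things follow if the table is programmed as printed:

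1. Complete MASES examinations are removed from the change analyses whenever ASDAS cannot be computed.
2. The MASES and SPARCC score rows carry no limit on missing sites and no proration. A partly completed examination could enter as a raw partial sum and look like improvement.
3. SPARCC, TJC and SJC change are governed by an observed-only rule, although a change also needs a baseline.

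**Working it through.** **Step 1: reproduce the plan's cut-offs.** The rule is more than 20% of sites missing. For 13 sites, 2/13 = 15.4% and 3/13 = 23.1%, so the limit is 3. For 16 sites, 3/16 = 18.75% and 4/16 = 25.0%, so the limit is 4. Both match the printed figures and tie each rule to its own score.

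**Step 2: compare each row's printed rule with the one printed two rows lower.** B/O means missing if baseline or observed value is missing; O means missing if observed value is missing.

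| Variable | As printed | Printed two rows lower |
|---|---|---|
| ASDAS clinically important improvement | blank | ASDAS B/O |
| ASDAS major improvement | blank | ASDAS B/O |
| MASES score | ASDAS B/O | 13-site rule |
| MASES change | ASDAS B/O | B/O |
| MASES = 0 | 13-site rule | O |
| SPARCC enthesitis score | B/O | 16-site rule |
| SPARCC change | O | B/O |
| SPARCC = 0 | 16-site rule | O |
| TJC total | B/O | half-of-joints rule |
| TJC = 0, baseline above 0 | O | O |
| TJC = 0, peripheral arthritis | half-of-joints rule | O |
| TJC change | O | B/O |
| SJC total | O | half-of-joints rule |
| SJC = 0, peripheral arthritis | B/O | O |
| SJC = 0, baseline above 0 | half-of-joints rule | O |
| SJC change | O | B/O |
| Anterior uveitis | O | NA |

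The rule each variable needs was read from its own derivation: a component rule for a score, B/O for a change, O for a zero-score response, and an ASDAS rule for an ASDAS response. Every entry in the right-hand column fits (17 of 17). As printed, only TJC = 0 with baseline above 0 fits (1 of 17). A move of one row fits 3 of 17, three rows 3 of 16, and four rows 1 of 15. The displacement is therefore two rows.

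**Step 3: does proration matter where it is printed?** In a zero-score row, 0 × 13/(13 − k) = 0 for any k missing sites, and a positive sum stays positive. Proration changes nothing there. It changes the score itself.

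**Step 4: size of an unprorated sum.** If k of n sites are blank, and blank sites are as likely to be active as scored ones, the plain sum misses k/n of the expected total. For MASES with 2 blank sites that is 2/13 = 15%. With 4 active sites among the 11 scored, the plain sum is 4 and the prorated sum is 4 × 13/11 = 4.73. For SPARCC with 3 blank sites and 5 active, the plain sum is 5 and the prorated sum is 5 × 16/13 = 6.15.

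**Step 5: size of the loss through ASDAS.** The share of MASES values lost equals the share of visits with a complete MASES but no ASDAS. The documents give no such rate. If it were 2% to 5% (an assumption), at most 100 × 0.02 = 2 to 100 × 0.05 = 5 values per group would go at a visit, from the planned 100 patients per group. Fewer would go in practice, because only patients with baseline MASES above zero are analysed. The Schedule of Activities collects CRP, Patient Global and BASDAI at every enthesitis visit, so the loss would come from missed samples or items and not from the visit plan.

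**The case against.** The strongest reply is that this is a clerical slip which any programmer would see through. The misplaced rules name their own denominators, 13 and 16, and speak of an imputed sum, so their target is plain. Several parts of the reply stand:

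- **Non-evaluable sites.** The MASES derivation cell scores them 0. That rule is separate from the displacement, and moving the column does not change it. The 15% figure can apply only to sites left blank.
- **ASDAS improvement rows.** Both depend on ASDAS change, which has its own baseline-or-observed rule, and both are analysed with NRI. The blank cells have little effect.
- **Joint counts.** The TJC and SJC total cells already adjust for evaluable joints and refer to Appendix 4, which is not readable in the public copy and may hold the rest.
- **Reach.** Only other secondary analyses, without multiplicity control, are involved.

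Text taken from a PDF table can also slip, and the BASMI and Jenkins sleep rows are visibly broken. That is an unlikely explanation here. The offset stays at two rows across several repeated page headings, ASDAS wording appears on the MASES page, and the MRI rows below are aligned again. The published PDF page should still be checked.

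What the reply does not remove is the rule beside MASES itself. It is a stated derivation rule, it is wrong for that variable, and no other readable text gives a competing rule for the MASES score.

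**Conclusion.** The point holds for the current table. From ASDAS clinically important improvement to the NSAID rows, the missing-data entries are two rows too low. The main consequence is that MASES and its change are made missing by ASDAS, which would discard valid data from a stated other secondary endpoint. The secondary consequences are that the 13-site and 16-site rules stand against the zero-score rows instead of the scores, and that three change variables have an observed-only rule.

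The size cannot be fixed from the documents. The 15% under-count per affected examination assumes blank, not non-evaluable, sites that are as likely active as the others. The loss through ASDAS equals an unstated rate of missing CRP or questionnaire items.

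A reader might infer more, and the documents do not support it:

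- That the enthesitis scores have no missing-site rule at all. The rules are printed within the MASES and SPARCC blocks, against the wrong rows.
- That key results are at risk. ASAS40, the major secondary endpoints and the MRI rows are not displaced. The ASDAS <2.1 cell is also blank, but the two-row move does not involve it.
- That the Revision History proves the fault. It describes superseded text and only shows that this table has slipped this way before. The finding rests on the current rows.
- That reported outputs are wrong. The intended rules may have been programmed, in which case the SAP and the analysis differ.

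**What to change.** Move the last-column entries up two rows, from ASDAS clinically important improvement through anterior uveitis. The result is the right-hand column of the table above:

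- the ASDAS rules on the two ASDAS improvement rows
- the 13-site rule on the MASES score and the 16-site rule on the SPARCC enthesitis score
- the half-of-joints rule on the TJC and SJC totals
- baseline-or-observed on the change rows and observed on the zero-score rows.

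State the intended rule for the NSAID rows, which the move leaves without one.

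Reconcile the scoring of non-evaluable MASES sites as 0 with the 13-site missing rule, so that it is clear which sites count as missing. Realignment alone does not settle this.

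First confirm the layout on the published PDF page. Then check the analysis dataset specification and the Week 16 and Week 52 outputs against the corrected table, and rerun the enthesitis analyses only if the printed rules were programmed.

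The cost is one table correction and a programming check. No new data are needed.
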